9.7 Safety and Other Analyses

The Safety Analysis Set will be used for summary and analysis of the safety endpoints.

9.7.1 Primary Safety Endpoint

Evaluation of overall safety, which includes the following:

- Subject reported AEs and SAEs from baseline through 24 months post-treatment, including adverse events of special interest (i.e., AEs of worsening low back pain)
- Laboratory tests (hematology, serum chemistry, inflammatory markers and antibody analysis). Abnormal results will be assessed relative to normative ranges and shift tables from baseline through 24 months post-treatment
- Reported events from radiographic imaging from baseline through 24 months posttreatment, including disc height at the treated level
- Post-treatment interventions affecting the treated disc through Visit 8 (24 months posttreatment) (comparison of the proportion of subjects in each group with an adjudicated post-treatment intervention at the treated level, and the proportion of subjects in each group with an adjudicated post-treatment intervention any lumbar level)
- Vital signs (heart rate, blood pressure and temperature) and body measurements (height, weight and BMI)
- Physical examinations (abbreviated).
- Neurological examinations (motor, sensory, reflex).

[figure not shown]
Descriptive statistics will be used for the summary of safety parameters – the number and percentage will be used for the incidences of AE/SAEs, deaths, early discontinuation due to AEs, and post-treatment interventions. The AE/SAE severity and relationship with the study procedure and treatment will be summarized and presented.

The mean, standard deviation/error, minimum, median, and maximum will be used for the laboratory parameters. The shift table (cross-tabulation) for the changes from baseline (low/normal/high) for the laboratory parameters will also be also provided and the test for treatment difference.

[figure not shown]
Safety parameters of special interest (i.e., AEs of worsening low back pain) will be summarized through 24 months post-treatment by treatment arm, severity, and the time from the study injection to the start of the AEs (0 to \leq 7 days, >7 days to < 3 months, \geq 3 months to 24 Months).

The incidence of this special interest AE (worsening low back pain) occurring within 3 to 24 months after study treatment will be also summarized, by treatment arm, for the responders and non-responders of the Primary Efficacy Endpoint.

The actual low back pain VAS score, the changes from the baseline and the responders with at least 50% reduction of low back pain VAS score at the time which the AEs of low back pain occurs will be summarized for each treatment, and the subject data listing will be presented for clinical review and assessment. Shift tables of changes in opioid use from the baseline to the time of AE onset will be also presented.

CONFIDENTIAL

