	 treatment To evaluate the Treatment Success at 24 months of rexlemestrocel-L alone or rexlemestrocel-L+HA based upon a composite responder analysis of low back pain Visual Analogue Scale (VAS) score, Oswestry Disability Index (ODI) score and no post-treatment interventions at the treated level. To evaluate the effectiveness of rexlemestrocel-L alone or rexlemestrocel-L+HA in reducing chronic low back pain based on incidence of subjects with minimal to no low back pain and no post-treatment interventions at the treated level at 24 months post-treatment (Minimal Pain Responder analysis) To evaluate the effectiveness of rexlemestrocel-L alone or rexlemestrocel-L+HA in improving function based on incidence of subjects with minimal to no low back pain and no post-treatment (Minimal Pain Responder analysis) To evaluate the effectiveness of rexlemestrocel-L alone or rexlemestrocel-L+HA in improving function based on incidence of subjects with minimal disability and no post-treatment

Clinical Study Protocol Study MSB-DR003

[figure not shown]

Version 7.0

	groups compared to the control group at 24 months.
Study Design	Prospective
	Multicenter
	Double Blind
	Placebo (defined as saline) controlled
	• Randomization,
	with the randomization ratio of 1:1:1 between
	a. Treatment Arm 1: approximately 6 million rexlemestrocel-L
	cells alone
	b. Treatment Arm 2: approximately 6 million rexlemestrocel-L
	cells + HA
	c. Treatment Arm 3: saline
	• Subjects will be followed for approximately 36 months post-treatment
	and evaluated at baseline, treatment day (Day 0), 1, 3, 6, 12, 18, 24 and
	36 months post-treatment. The primary endpoint for evaluation of
	safety and effectiveness will be conducted at 24 months. Longer-term
	safety and effectiveness assessments will be conducted at 36 months.
	• It is strongly recommended that there be no changes (increase or
	decrease) from or additions to baseline pain medications (opioids,
	NSAIDs, aniline analgesics, etc.) through at least the 24 month
	primary endpoint follow-up. This is designed to minimize possible
	confounding treatment effects due to alterations in pain medications.
	Furthermore, it is suggested that subjects do not schedule any medical
	procedures which would require an adjustment in pain medications
	during the 2 weeks prior to any study visit. Subjects not taking opioids
	at baseline should similarly refrain from starting opioid treatment.

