	The DSMB will be unblinded in order to assess the safety of investigational product (IP).
	The TEC performing adjudication of post-treatment interventions at the treated disc and relationship of adverse events to the product or procedure will be blinded to treatment assignment.
	When the unblinded statistical analyses are conducted at the primary safety and efficacy evaluation (the 24-month safety and efficacy evaluation period), study subjects, as well as site personnel responsible for subject care and assessment, radiographic reviewers and TEC members, will continue to be blinded until completion of the study at 36 months post- treatment.
	An unblinded statistician will conduct the specified interim analyses and only the information prescribed in the SAP will be provided so as to maintain the blind.
Duration of	This is a one-time treatment administration.
Treatment	
Follow up	All subjects will be followed for 36 months post-treatment. Subjects will
Schedule	be evaluated at baseline, treatment day (Day 0), as well as Study Visits 3,
	4, 5, 6, 7, 8, and 9 (corresponding to 1, 3, 6, 12, 18, 24, and 36 months
	post-treatment). The primary analysis of safety and efficacy will be assessed at Visit 8 (24 months post treatment). A longer term follow up
	assessed at Visit 8 (24 months post-treatment). A longer-term follow-up of safety and efficacy will be assessed at Visit 9 (36 months post-
	treatment).
Data & Safety	A DSMB will meet on a regular basis and ad-hoc, as needed, to review
Data & Salety	A DSIMB will meet on a regular basis and au-noe, as needed, to review

[figure not shown]
Monitoring	safety, enrollment progress, and any other pertinent information. The
Board	DSMB will consist of an independent multi-disciplinary group. Based on
	its findings, the DSMB will make recommendations regarding study
	continuation, enrollment and/or study modification(s).
Post-Treatment	Surgical and injection interventions should be avoided through at least
Interventions	the 24 month primary endpoint follow-up. Surgical and injection
	interventions should only be undertaken if the subject's pain, measured by
	VAS, and function, measured by ODI, are not improved compared to the
	baseline values since an intervention could confound the efficacy
	assessments and would classify a subject as a treatment failure.
	For any subjects who are planning any post-treatment intervention during
	the course of the study, every effort should be made to schedule an

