6. STUDY PROCEDURE

6.1 Visit Schedule and Assessments

Table 3 shows all planned assessments, which are marked with an "X" for the visits at which they are performed. Subjects should be seen for all visits on the designated days or within the given windows for those visits. The study assessment schedule outlines all procedures to be performed on subjects at the scheduled visits.

In order to minimize variability in evaluations, ideally, the same personnel should perform the same tests and assessments on all the subjects at a given trial site, if possible.

Sites are required to access the interactive web response system (IWRS) at the beginning of the screening period to obtain a screening number. Sites are also required to access IWRS at the conclusion of the screening period to register the subject status. If the subject does not meet all inclusion and exclusion criteria, the subject will be considered a screen failure. If the subject meets all inclusion and exclusion criteria, the subject must be randomized a minimum of 7 days prior to treatment (Day 0) to allow time for shipment of investigational product to the site. In addition, treatment must be administered no later than 30 days following randomization.

Assessment	Screen/ Baseline ^b Visit 1 Days -105 to 0 ^a	Visit 2 Day 0 Treatment Injection ^w (7-30 days post- Randomiz ation)	Visit 3 1 Month (± 14 Days) ^a	Visit 4 3 Months (± 14 Days) ^a	Visit 5 6 Months (± 30 Days) ^a	Visit 6 12 Months (± 60 Days) ^a	Visit 7 18 Months (± 60 Days ^a	Visit 8 24 Months (± 60 Days ^a	Visit 9 36 Months (± 60 Days ^a	Unscheduled Visit ^c
Informed consent and privacy forms (e.g., HIPAA) ^d	Х	—	—	—	—					
Inclusion/exclusion criteria	Х	Х		_						
Demography and smoking history	X	_			_					
Medical & surgical histories	X				_					
Alcohol and Substance Abuse	X									
Questionnaire										
Mental Illness/Incompetence	Х									
Questionnaire										
Pain Catastrophizer Scale	Х									
SCORE or MORES assessment	X °									
Disease targeted, abbreviated PE e	Х	Х	Х	Х	X	X	Х	Х	Х	
Neurological Examination	Xf	X g	Х	Х	Х	Х	Х	Х	Х	Х
Targeted PE to rule out SI joint pain h	Х									
Vital signs, seated, if possible	Х	Xi	Х	Х	Х	Х	Х	Х	Х	Х
Height, weight, and BMI	Х	Х	Х	Х	Х	Х	Х	Х	Х	Х
Hematology	Х	—	Х	_	_	Х		Х	Х	
Chemistry Panel	Хj	—	Х	—	_	Х		Х	Х	
HIV	Х		_	_	_	_				
Pregnancy Test ^k	Х	X	_	_	_	_				
Flow Class I and II % PRA with specificity testing and DSA ¹	Х		—	—	—	Х		Х	Х	
MRI scan ^m	Х	_	_	_	_	Х	Х	Х	Х	

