6.1.1 Screening Period

A subject will enter the screening period once a written informed consent has been signed by the subject. In addition, all subjects must sign a HIPAA authorization or other local regulatory agency required form as applicable for use, collection, and disclosure of PHI.

This initial screening period will not exceed 105 days (75 day screening period until randomization and a maximum of 30 days between randomization and study treatment). During the screening period it will be determined that the subject meets all inclusion and exclusion criteria. Baseline assessments will also be completed during this time. All patient-reported outcomes (including VAS and ODI assessments), as well as baseline use of pain medication (i.e., 2-week e-diary record), will be established during screening. All such assessments should be performed prior to the diagnostic disc injection to confirm intact annulus or discography, if deemed necessary. However, if the subject had received a previous diagnostic injection procedure to confirm intact annulus or discography prior to the screening period (but within the permitted timeframes to serve as the baseline evaluation; see Section 4.2.2), these patient-reported outcomes and e-diary entries must be started at least 14 days following the most recent injection procedure.

A neurological exam will be performed prior to the diagnostic injection to confirm an intact annulus or discography and again after the procedure. If a recent diagnostic injection or discography taken before the screening period serves as the baseline evaluation for a subject, the pre-injection neurological exam may be waived, though a neurological exam will need to be performed prior to any additional invasive procedures or the treatment injection. This neurological exam will be used as the subject's baseline neurologic status.

If a subject is re-screened, most patient-reported outcomes must be completed again at least 2 weeks after the most recent diagnostic injection procedure. These patient-reported outcomes include VAS assessments (leg and low back pain), ODI questionnaire, EQ-5D, and iPCQ. However, if an e-diary was collected during a previous screen, this may be used, provided it meets all criteria for a valid e-diary collection (i.e. 10 out of 14 days pain medication usage collected).

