7. SAFETY GUIDANCE

7.1 Definitions

7.1.1 Adverse Event

According to the International Conference of Harmonization [ICH] guideline for Good Clinical Practice, an AE is any untoward medical occurrence in a patient administered a pharmaceutical product and which does not necessarily have a causal relationship with this treatment. An AE can therefore be any of the following:

- Unfavorable and unintended sign (including an abnormal laboratory finding), symptom, or disease temporally associated with the use of a medicinal (investigational) product, whether or not considered related to the medicinal (investigational) product.
- Any new disease or exacerbation of an existing disease (a worsening in the character, frequency, or severity of a known condition)
- Recurrence of an intermittent medical condition (e.g., headache) not present at baseline
- Any deterioration or abnormality in a laboratory value or other clinical test (e.g., ECG, X-ray) that is associated with symptoms or leads to a change in study treatment or concomitant treatment or discontinuation from study drug
- Adverse events that are related to a protocol-mandated intervention, including those that occur prior to assignment of study treatment (e.g., screening procedures such as biopsies etc.).

Adverse events will be captured following signing of the informed consent form. Pre-existing conditions (i.e., medical history) which **worsen** during a study are to be reported as AEs.

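### The AE/SAE window of the primary safety endpoint opens at baseline, up to 105 days before injection, while Section 6.1.3 starts the primary safety period at the Day 0 injection

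*Combined protocol and SAP*

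**What the plan says.** Section 9.7.1 lists the components of the primary safety endpoint. The first is "Subject reported AEs and SAEs from baseline through 24 months post-treatment, including adverse events of special interest".

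Baseline is not the injection day:
- The synopsis (follow-up schedule) has subjects "evaluated at baseline, treatment day (Day 0), as well as Study Visits 3", so baseline and Day 0 are separate timepoints.
- The schedule of assessments (Table 3) heads the first column "Screen/ Baseline ^b Visit 1 Days -105 to 0 ^a"; the injection is Visit 2.
- Section 6.1.1 places the baseline assessments within screening and adds: "This initial screening period will not exceed 105 days".

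On collection, Section 7.1.1 states: "Adverse events will be captured following signing of the informed consent form". Its AE definition covers events related to protocol-mandated interventions, "including those that occur prior to assignment of study treatment".

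Two other places use a different clock. Section 6.1.3 dates its evaluation period from Day 0 to 24 months and says that the Day 0 injection begins the primary safety and efficacy period. Section 2.5 sets the primary safety objective as the safety of a single injection through 24 months after treatment. Within Section 9.7.1 itself, back-pain AEs of special interest (AESIs) are also summarized in bands timed from the study injection.

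**The concern.** A by-arm AE incidence is meant to show what followed the injection. An event that began before the injection cannot have been caused by it, and under randomization such events are on average equally frequent in all three arms. If they are counted, they raise every arm's percentage and pull the arms together. In a safety comparison, that makes a real excess harder to see.

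The pre-injection period here is not empty. Screening can include a medial branch block, a contrast injection into the disc, and possibly a sacroiliac joint injection or discography. The Safety Analysis Set (Section 9.3.6) does not help: it restricts which subjects are counted, not when their events began.

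The tables may also fail to agree. A back-pain AE after a screening disc injection falls inside the endpoint window but in none of the injection-timed bands.

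**Working it through.** **1. The plan's own figure.** Section 6.1.1 allows up to 75 days from the start of screening to randomization and up to 30 days from randomization to treatment: 75 + 30 = 105 days. This agrees with the stated maximum and with Table 3. Taking 24 months as 730 days, the longest possible pre-injection share of the window is 105 / (105 + 730) = 12.6%. That is a share of calendar time at the maximum, not a share of events.

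**2. Which texts conflict.** Section 9.7.1 starts at baseline (Visit 1, Days -105 to 0). Section 6.1.3 starts at the injection, and Section 2.5 concerns the injection. The back-pain bands in Section 9.7.1 start at 0 days from injection, and the time-to-intervention analysis in Section 9.6.3 also runs from the injection. The general AE/SAE component is the one that does not fit.

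**3. Effect on subject-level incidence.** Let p be the proportion of subjects with an AE after injection and q the proportion with one before it. Assume that q is equal across arms and independent of later events. Then

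- observed incidence = 1 - (1-q)(1-p)
- observed risk difference = (1-q) × true risk difference

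The documents give neither p nor q for all AEs, so both are assumed. For post-injection rates of 50% vs 60% (difference 10 points, ratio 1.20):

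| q | Observed rates | Difference (points) | Ratio |
|---|---|---|---|
| 1% | 50.5% vs 60.4% | 9.9 | 1.196 |
| 10% | 55% vs 64% | 9 | 1.16 |
| 20% | 60% vs 68% | 8 | 1.13 |
| 30% | 65% vs 72% | 7 | 1.11 |

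The difference shrinks by the same factor at any event rate. The ratio suffers more when post-injection rates are low. For an assumed 10% vs 25% (ratio 2.50), it falls to 2.36 at q = 1%, 1.71 at q = 10% and 1.43 at q = 20%.

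**4. What is not affected.**
- *Event counts:* with an assumed 1.5 vs 2.0 events per subject and 0.2 pre-injection events added to each arm, the difference stays 2.2 - 1.7 = 0.5. Only the ratio moves, from 1.33 to 1.29.
- *Back-pain AESI bands:* timed from injection, so q = 0.
- *Post-treatment interventions:* after injection by definition.

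**The case against.** The strongest reply is that Section 6.1.3 already fixes the primary safety period at the injection, so the endpoint wording is merely loose. The same phrase appears elsewhere in Section 9.7.1 for laboratory shift tables, where baseline is a reference state rather than a start date. Section 7.1.1 governs which AEs are captured, not which enter the between-arm tables. Part of this stands: the plan shows no deliberate decision to count pre-injection events. But for AEs and SAEs the text gives a start and an end, and a programmer following it would include those events.

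The detailed SAP text is not visible, and parts of Section 9.7 are withheld. A reader might infer that the plan has no treatment-emergent rule; that cannot be asserted. The visible uses of the term do not settle the matter. Section 12.1 applies it to safety reports for the DSMB, and Section 7.5 applies it to laboratory results from tests done after consent.

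The size is assumed, which is correct. The nearest documented figure is in Section 1.7.8, which puts discography complications below 1%. That covers complications rather than all AEs, but it supports showing a low end where the effect is negligible. Acceptable earlier screening injections need not be repeated, and eligibility rules will remove some subjects with serious screening events, so q is probably lower for SAEs.

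The summary by relationship to procedure and treatment separates some of these events. It does so only partly, because study procedure is not clearly limited to the treatment injection.

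**Conclusion.** This is an internal inconsistency worth correcting. Section 9.7.1 opens the AE/SAE window before the injection, while Section 6.1.3 and the primary safety objective point to the injection. Under the literal wording, subject-level risk differences keep a fraction (1-q) of their size: a 1% to 30% loss for assumed q of 1% to 30%. This rests on q being equal across arms and independent of later events, and on the AE percentages being subject-level.

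Three stronger readings are tempting and are not supported:
- *Every safety comparison is diluted.* The AESI bands, interventions and absolute differences in event counts are not.
- *A planned safety test loses power.* AE summaries are descriptive, and the visible text gives no test for AE incidence.
- *The product is made to look safer.* The effect is attenuation toward no difference. It would hide an excess in an active arm, but it would equally hide an advantage. It does not favor one arm by design.

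**What to change.** In Section 9.7.1, define the AE/SAE component as events with onset or worsening at or after the start of the study injection (Day 0) through 24 months. This agrees with Section 6.1.3 and the AESI bands. Use that definition for all between-arm AE/SAE summaries, and tabulate events from consent to injection separately so that the safety of the screening procedures is still reported. If the SAP already has a treatment-emergent definition, align the protocol wording with it.

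The cost is one phrase and one extra table. No new data are needed, because onset timing is already required for the AESI bands.

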9.8 Interim Analyses

Interim analyses may be performed during the course of the trial. These will be conducted by external independent statistician(s) who will be unblinded to study data. All blinded personnel and subjects will remain blinded to the results of the analyses. The integrity of the study database will be maintained as well, and no bias will be introduced to the evaluations in the study due to the conduct of these interim analyses.

The details of interim analyses are outlined in the Statistical Analysis Plan (SAP). All subjects, independent reviewers and blinded personnel interacting with subjects will remain blinded through the completion of the study.

9.9 Handling of Missing Values, Early Termination, or Non-Interpretable Data

For the responder analyses, including the primary efficacy endpoint, as well as pain and function responder analyses, subjects will be classified as having attained success (responder) or not attained success (non-responder).

The Primary Efficacy Endpoint requires a subject to meet clinically significant improvements in both pain and function at both 12 and 24 months, as well as not undergo any post-treatment intervention at the treated level through 24 months, to be considered a success.

If in-clinic assessments for Study Visits 6 and 8 (corresponding to 12 and 24 months) are unavailable, the data will be considered missing. If a scheduled in-clinic visit is missed, the site should contact the subject to determine if any interventions that would classify the subject as a treatment failure have occurred since their last visit. If any interventions are reported, the site should collect all the information required if the intervention had been reported at an in-clinic visit. All intervention information collected remotely must be documented in a source document and/or worksheet.

If a subject receives a post-treatment intervention at the treated level on or prior to the date of Study Visit 8 (24 months), this subject will be considered a non-responder regardless if there is any missing data. For example, a subject that has a post-treatment intervention at the treated level at the time of Study Visit 4 (3 months) would be considered a non-responder regardless of whether there are Visit 6 or Visit 8 data available for analysis, as they would have already failed one of the criteria to be considered a responder.

If a subject has data available at both Study Visit 6 (12 months) and Study Visit 8 (24 months), with no post-treatment intervention at the treated level as of the date of Study Visit 8, that subject will be determined either a responder or non-responder based upon whether or not the subjects meets the pain and functional improvement criteria at both study visits.

Any subject that is missing one or more components in an endpoint (e.g. VAS in the primary endpoint) at a visit will be considered a non-responder at that visit if any available component of the endpoint indicates that the subject is a non-responder (even if all components of the endpoint are not available). If none of the available components impose non-response, the outcome will be considered missing and will be handled according to the proposed methodology described below.

Assumptions regarding responder analyses include the following:

- If the subject does not meet the criteria of either pain or function at either Visit 6 or Visit 8, the subject will be considered a non-responder.
- If the subject meets the pain and function improvement criteria at both Visit 6 and Visit 8, and has no post-treatment intervention as of the date of Visit 8, the subject will be considered a responder.

- Any subject that is a non-responder on one of the two primary study visits (Visit 6 or Visit 8) but has a missing outcome for the other study visit is deemed a non-responder and not considered to have a missing outcome for the primary analysis.
- If a subject does not have a minimum of a visit at 3-months (Study Visit 4) they will be considered a non-responder.
- Any subject that has a minimum of 3-months data (Study Visit 4) but is missing one or both of the two primary study visits, will have their outcome multiply imputed based on their available information. Separate models will be constructed for
 - Subjects that are missing one of the two primary study visits (Visit 6 or Visit 8) but not both;
 - \circ Subjects that are missing both of the primary study visits.

A detailed description of the statistical methodology for multiple imputation of missing data for responder analyses can be found in the SAP.

For subjects who have a post-treatment interventional procedure at the treated level, the analyses of continuous and categorical efficacy variables will include only data collected before the post-treatment adjudicated intervention.

MMRM will be used for the analysis of over time of quantitative variables and missing data will not be imputed.

The SAP provides additional details regarding methods for handling missing data.

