6.3 Missing or Delayed Study Visits

Subjects should be encouraged not to miss any visits. Any visits that are missed or not completed within the specified timeframe (or window allowance) should be documented by the site and the CRA should be notified.

If a scheduled in-clinic visit is missed, the site should contact the subject to determine if any interventions that would classify the subject as a treatment failure have occurred since their last visit. If any interventions are reported, the site should collect all the information required if the intervention had been reported at an in-clinic visit. All intervention information collected remotely must be documented in a source document and/or worksheet.

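### Section 9.9 classes a subject who misses Visit 4 but succeeds at Visits 6 and 8 as both responder and non-responder, with no order of precedence

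*Combined protocol and SAP*

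**What the plan says.** Three statements in protocol section 9.9 bear on the same subject.

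- **Complete data.** For a subject with data at both Visit 6 (12 months) and Visit 8 (24 months) and no intervention at the treated level, "that subject will be determined either a responder or non-responder based upon whether or not the subjects meets the pain and functional improvement criteria"; this is judged at each of those two visits.
- **Second bullet of the responder list.** "If the subject meets the pain and function improvement criteria at both Visit 6 and Visit 8", with no post-treatment "intervention as of the date of Visit 8, the subject will be considered a responder".
- **Fourth bullet of the same list.** "If a subject does not have a minimum of a visit at 3-months (Study Visit 4) they will be considered a non-responder".

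The fifth bullet sends some subjects to multiple imputation and states whom it covers: "Any subject that has a minimum of 3-months data (Study Visit 4) but is missing one or both of the two primary study visits". The fourth bullet has no such limit.

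The synopsis repeats these rules. The primary endpoint definition in section 9.4.1 refers to Visits 6 and 8 only and sets no Visit 4 requirement. Section 9.9 refers to the SAP for the imputation method and for further missing-data detail, but no SAP text is readable in the supplied file.

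**The concern.** Read as written, the fourth bullet covers every subject without a 3-month visit, including one whose 12- and 24-month outcomes were both observed and both successful. The complete-data rule and the second bullet call that subject a responder.

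The list governs the responder analyses, including the primary endpoint. If the fourth bullet is programmed literally, an observed success is scored as a failure, contrary to the definition in section 9.4.1. Two programmers working from section 9.9 could derive different primary outcomes from the same data. A choice between the two readings made after unblinding could look data-driven.

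**Working it through.** **Step 1: does any pattern receive two outcomes?** Take Visit 4 as attended or missed, and Visits 6 and 8 each as success, failure or missing, with no intervention. That gives 2 × 3 × 3 = 18 patterns. Applying each rule in section 9.9:

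| Visit 6 / Visit 8 | Visit 4 attended | Visit 4 missed |
|---|---|---|
| success / success (1 pattern) | responder | **responder** (complete-data rule, second bullet) **and non-responder** (fourth bullet) |
| both observed, at least one failure (3) | non-responder | non-responder |
| one failure, one missing (2) | non-responder | non-responder |
| at least one missing, no failure (3) | multiply imputed | non-responder (fourth bullet) |

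The third row follows the list's third bullet, which treats such subjects as not having a missing outcome and so keeps them out of imputation. Seventeen patterns get one outcome. One gets two.

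**Step 2: does the text give an order?** The only override wording in section 9.9 is "this subject will be considered a non-responder regardless if there is any missing data", and it concerns post-treatment interventions. Nothing comparable is attached to a missed Visit 4.

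**Step 3: can the pattern occur?** Yes. Section 6.3 says "If a scheduled in-clinic visit is missed, the site should contact the subject to determine if any interventions" have occurred; it does not withdraw the subject. Table 3 allows ±14 days for Visit 4 and ±60 days for Visits 6 and 8, so the 3-month window is the tighter one.

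**Step 4: what about the Visit 8-only responder endpoints?** Secondary endpoints 3 to 5 in section 9.4.2 are defined on Visit 8 without a Visit 4 condition. The complete-data rule and second bullet concern both visits, so the conflict here is between the fourth bullet and the endpoint definitions themselves. A subject who meets the Visit 8 definition but missed Visit 4 is a success under one and a non-responder under the other.

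**Step 5: size.** The plan gives no figure to reproduce. Inputs:

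- From the protocol: about 120 per arm (section 3.1), here all taken as analysed; Beta(0.5, 0.5) priors (section 9.6.2); threshold 0.9875 (section 9.6.3), which equals 1 − 0.025/2.
- Assumed: that 0.9875 also applies to the primary comparison (section 9.6.2 leaves that value to the SAP); the response rates; the share m who miss Visit 4.

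Success is P(active rate > saline rate | data) > 0.9875, evaluated over all 121 × 121 possible results. Literal use of the fourth bullet replaces each arm's response rate p by p × (1 − m). This treats missing Visit 4 as unrelated to response and assumes both later visits are observed.

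Power at 25% saline versus 42% active:

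| m | Power |
|---|---|
| 0% | 0.718 |
| 1% | 0.711 |
| 2% | 0.704 |
| 5% | 0.682 |
| 10% | 0.644 |

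Expected successes recoded at m = 2%: 120 × 0.42 × 0.02 ≈ 1.0 active and 120 × 0.25 × 0.02 = 0.6 saline.

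One-sided type I error per comparison, 30% response in both arms:

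| Miss Visit 4, active / saline | Error |
|---|---|
| equal (0%, 2% or 5%) | 0.0129 |
| 1% / 3% | 0.017 |
| 3% / 1% | 0.010 |
| 2% / 8% | 0.027 |
| 8% / 2% | 0.006 |

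Effect of recoding one active responder at the smallest winning count, 120 per arm:

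| Saline responders | Active responders | Posterior probability |
|---|---|---|
| 24 | 40 → 39 | 0.9904 → 0.9863 |
| 30 | 47 → 46 | 0.9908 → 0.9870 |
| 36 | 53 → 52 | 0.9886 → 0.9841 |

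Each pair crosses 0.9875.

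**The case against.** The strongest reply is that context makes the intent plain. Section 9.9 is about missing data. It settles complete cases first and then turns to outcomes that remain missing. The fourth and fifth bullets look like a pair: without a 3-month visit the subject is a non-responder; with one, but lacking a primary visit, the subject is imputed. On that reading a subject with complete Visit 6 and Visit 8 data never reaches the fourth bullet. This is probably what was meant. It needs a qualifier, however, that the fifth bullet has and the fourth lacks.

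Second, the SAP may settle the order. That stands: the claim is confined to section 9.9 and the synopsis, and the harm arises only if the SAP does not resolve the point. Two opposite classifications in the protocol should still be reconciled there.

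Third, the numbers rest on assumed rates. This also stands. At 1% to 2% missed, power falls by only about 0.7 to 1.5 percentage points. The 0.027 error needs a fourfold imbalance between arms, which nothing in a trial with blinded subjects and assessors suggests. Any threshold test can turn on one subject. The figures show scale and are not forecasts; the contradiction does not depend on them.

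**Conclusion.** The concern holds. Section 9.9 and the synopsis give two opposite outcomes for one reachable pattern: Visit 4 missed, success at Visits 6 and 8, no intervention. The readable text sets no precedence.

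The number of subjects is unknown and probably small. Under the assumptions above, literal use of the fourth bullet costs about 1.5 percentage points of power at 2% missed and 3.6 at 5%. It leaves type I error unchanged when missingness is equal, and moves it in either direction when it is not. Confidence is high on the wording. The effect on the analysis is conditional on the SAP and on the rates that occur. Because this is the derivation of the primary endpoint and the repair is trivial, it should be fixed, although it does not threaten the design.

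**What to change.** In section 9.9 and the synopsis, and in the SAP if it repeats the rule, state that observed Visit 6 and Visit 8 outcomes take precedence, and limit the fourth bullet. Suggested wording: *If the outcome is not determined by observed Visit 6 and Visit 8 data and the subject has no Visit 4, the subject will be considered a non-responder.* For the Visit 8-only responder secondaries, use the same clause with Visit 8 alone.

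The cost is one clause, agreed before unblinding. It needs no new data and leaves the imputation population unchanged. Whether subjects with later visits but no Visit 4 should be imputed instead is a separate, optional choice for the sponsor.
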